12.2.4.1 In-Home Study Visits

Where possible via in-home visits by study personnel or contracted vendor (where applicable), the following safety assessments should also be completed, in addition to the safety assessments above. **Note:** For any clinical laboratory determinations, specimen collection, handling and processing must be carried out in accordance with the central laboratory manual. Due to considerations of the processing time required, pharmacokinetic (PK) samples should not be collected during in-home visits. If processing cannot be completed within the time specified in the central laboratory manual for any other samples, collection of those samples should be omitted.

- Collection of samples for clinical laboratory assessments (in accordance with Table 3- Schedule of Clinical Laboratory Tests of the Global Protocol (Amendment #3) or Country-Specific Protocol, if applicable.)
- Serum pregnancy testing
- Electrocardiogram (ECG)
- Vital signs (with or without weight)
- Physical examination

12.2.4.2 Clinical Laboratory Assessments

All attempts should be made to complete clinical laboratory assessments, including pregnancy testing, in accordance with Table 3- Schedule of Clinical Laboratory Tests of the Global Protocol (Amendment #3) or Country-Specific Protocol, if applicable. As an alternative to patients having laboratory assessments on-site, or conducted via an in-home visit by study personnel, laboratory assessments may also be conducted at an alternate laboratory facility, if necessary (eg, general practitioner's office, commercial laboratory etc.). In this case, the data is intended to facilitate the safety oversight of the patient and will be filed in the source document only and not recorded in the eCRF. If a patient is unable or unwilling to travel to an alternate laboratory facility, the laboratory assessment at the scheduled timepoint may be omitted. For women of childbearing potential, study sites may provide urine pregnancy test kits for at-home testing. Study personnel should document the patient's verbal confirmation of pregnancy test results in the source document. Results of at-home urine pregnancy tests will not be recorded in the eCRF. Every attempt should be made to have patient complete as an Unscheduled assessment during the Safety Follow-up (SFU) period. Clinical findings upon termination must be followed until the condition returns to prestudy status or can be explained as unrelated to investigational product. If necessary, an additional follow-up visit should be scheduled.

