6.6.3 Clinical Laboratory Determinations

Clinical laboratory tests will be performed according to the schedule in [Table 3](#). Patients will be asked to fast for at least 10 hours prior to any visit requiring clinical laboratory testing.

Table 3 Schedule of Clinical Laboratory Tests

Category	Visit Number(s)	Parameter(s)
Hepatitis Serology	1	Hepatitis C virus antibody, hepatitis B surface antigen, and hepatitis B core antibody total. Reflex hepatitis B core antibody immunoglobulin M will be performed for all hepatitis B core antibody total positive or reactive results. Reflex HCV RNA titer test will be performed for all Hepatitis C virus antibody positive or reactive results.
Screening Hemoglobin A1c	1	Hemoglobin A1c
Hematology	1 and Visit 6/ET	Absolute and differential white blood cell count, Absolute Neutrophil Count (ANC), erythrocyte count, hemoglobin, hematocrit, platelet count, and red blood cell indices (mean corpuscular volume, mean corpuscular hemoglobin, and mean corpuscular hemoglobin concentration)
Chemistry	1 and Visit 6/ET	Sodium, potassium, calcium, chloride, bicarbonate, glucose, blood urea nitrogen, creatinine, total protein, alkaline phosphatase, albumin, total bilirubin, direct bilirubin, indirect bilirubin, AST, ALT, free T3, free T4, TSH, lactate dehydrogenase, creatine phosphokinase, γ -glutamyl transpeptidase, uric acid, phosphate, lipid panel (total cholesterol, triglycerides, low-density lipoproteins, high-density lipoproteins), prolactin, insulin, and magnesium
Urine drug screen	1	Benzoylecgonine (cocaine), barbiturates, amphetamines, benzodiazepines, cannabinoids, opiates, methadone, phencyclidine
Urine myoglobin	1 and Visit 6/ET	Only in patients with creatine phosphokinase levels > 1000 U/L or as clinically indicated for any rise in creatine phosphokinase levels or as necessitated by symptoms
Urinalysis	1 and Visit 6/ET	Specific gravity, pH, protein, glucose, ketones, blood, nitrite, bilirubin, and microscopy (red blood cell count [high-power field], white blood cell count [high-power field], casts [low-power field], and crystals)
Blood alcohol concentration	1	Blood alcohol concentration by Breathalyzer
Serum β -hCG (women of childbearing potential only)	1, Visit 6/ET, and Visit 7 Safety Follow-up Visit	—
Repeat urine drug screen, blood alcohol level, and serum pregnancy test	At random upon request from the Investigator	—

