6.7 Summary of Methods of Data Collection

An IWRS will be used to screen patients, dispense IP, randomize patients, and manage IP inventory. All other data for this study will be collected using eCRFs via an electronic data capture system, except for ECG and laboratory data.

A qualified central ECG and central laboratory vendor will be used for the analysis of all ECGs and blood and urine samples. ECG and laboratory data will be transferred to Allergan or its designee on a periodic basis throughout the study.

7 Statistical Procedures

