9.5 Potential Hy's Law Cases

Criteria for potential Hy's law cases are as follows:

- ALT or AST $\geq 3 \times$ ULN AND
- Total bilirubin $\geq 2 \times$ ULN AND
- Alkaline phosphatase $< 2 \times$ ULN

Study site personnel must report every patient who meets these criteria. Typically, all 3 analytes will be obtained from the same sample, but they may come from multiple samples taken within a 24-hour period. This requirement applies from the time the patient signs the ICF for the study until 30 days after last known dose of study treatment.

A laboratory alert for potential Hy's laws cases will be in place, and the laboratory must notify Investigators and the Sponsor (Allergan) immediately when the above criteria have been met. A potential Hy's law case must be reported to Allergan on an SAE/AESI Form as soon as possible (within 24 hours of learning of the potential Hy's law case) to the SAE/Pregnancy fax number, even if no AE has occurred. The eCRF for potential Hy's law cases must be completed within 7 calendar days. Every effort to determine the cause of the liver enzyme abnormalities must be made, and close monitoring should be initiated in conjunction with the Allergan Medical Monitor and in accordance with the FDA Guidance for Industry, Drug-Induced Liver Injury: Premarketing Clinical Evaluation, July 2009. The patient should return to the study site and be evaluated as soon as possible, preferably within 48 hours from the time the Investigator becomes aware of the abnormal results. This evaluation should include laboratory tests, detailed history, and physical assessment.

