10.2 CLINICAL LABORATORY PARAMETERS

Descriptive statistics for clinical laboratory values (in SI units) and changes from the baseline values at each assessment time point will be presented by treatment group for the following laboratory parameters:

Hematology:	Absolute and differential white blood cell count, erythrocyte count, hemoglobin, hematocrit, platelet count, and red blood cell indices (mean corpuscular volume, mean corpuscular hemoglobin, and mean corpuscular hemoglobin concentration)
Chemistry:	Sodium, potassium, calcium, chloride, bicarbonate, glucose, blood urea nitrogen, creatinine, total protein, alkaline phosphatase, albumin, total bilirubin, direct bilirubin, indirect bilirubin, AST, ALT, free T3, free T4, TSH, lactate dehydrogenase, creatine phosphokinase, γ -glutamyl transpeptidase, uric acid, phosphate, lipid panel (total cholesterol, triglycerides, low-density lipoproteins, high-density lipoproteins), prolactin, insulin, and magnesium
Urinalysis:	Specific gravity, pH

In addition, descriptive statistics for values and changes from the baseline values in conventional units at each assessment time point will be presented for selected clinical laboratory parameters listed in [Appendix II](#). A description of reporting the lab values in conventional units in participant narratives (along with the standard reporting in SI units) is presented at the end of [Appendix II](#). Only participants with clinical laboratory data at baseline and at least one postbaseline visit during the double-blind period will be included in the summary.

Laboratory tests values are considered to be potentially clinically significant (PCS) if they meet either the low or high PCS criteria listed in [Table 10-1](#). The number and percentage of participants with PCS postbaseline clinical laboratory values will be tabulated by treatment group. The percentages will be calculated relative to the number of participants with available non-PCS baseline values and at least 1 postbaseline assessment. The numerator will be the total number of participants with available non-PCS baseline values and at least 1 PCS postbaseline value. A supportive listing of participants with PCS postbaseline values will be provided, including the participant identification number, study center number, and baseline and postbaseline values. A listing of all AEs occurring in participants who have PCS laboratory values will also be provided.

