The number and percentage of participants with treatment-emergent significant changes in lipid parameters (total cholesterol, low-density lipoprotein cholesterol, high-density lipoprotein cholesterol, and triglycerides) and glucose will be tabulated by treatment group for the DB treatment period. The criteria for treatment-emergent significant changes in lipids and glucose is provided in [Table 10-2](#). Percentages will be calculated relative to the number of participants with baseline values meeting the specified baseline criteria and with at least 1 postbaseline assessment. The change in lipids and glucose from baseline to the highest (lowest for high-density lipoprotein cholesterol) postbaseline measurement will be summarized. Supportive listings of participants with treatment-emergent changes in lipids and glucose values will be provided.

The number and percentage of participants meeting potential Hy's Law criteria (elevation of alanine aminotransferase [ALT] or aspartate aminotransferase [AST] $\geq 3x$ ULN with total bilirubin [TBL] $\geq 2x$ ULN and alkaline phosphatase [ALP] $< 2x$ ULN in a 24-hour period) and Concurrent Elevations criteria in a 24-hour period will be tabulated by DB treatment group for the safety population. A supportive listing will be provided.

Concurrent Elevations in a 24-hour period are defined as:

1. ALT or AST $\geq 3x$ ULN and TBL $\geq 1.5 x$ ULN
2. ALT or AST $\geq 3x$ ULN and TBL $\geq 2 x$ ULN

Table 10-1 Clinical Laboratory PCS Criteria

Laboratory Parameter	SI Unit	PCS Criteria Low Values	PCS Criteria High Values
Hematology			
Hemoglobin	g/L	< 0.9 × LLN	—
Hematocrit	%	< 0.9 × LLN	—
Eosinophils	%	—	> 10
Neutrophils	%	< 30	> 90
Basophils	%	—	> 6
Monocytes	%	—	> 20
Lymphocytes	%	< 10	> 60
Absolute neutrophils	10 ⁹ /L	< 1.0	—
Platelet count	10 ⁹ /L	≤ 75	≥ 700
White cell count	10 ⁹ /L	≤ 2.5	≥ 15
Chemistry			
Albumin	g/L	< 0.9 × LLN	> 1.1 × ULN
Alkaline phosphatase	U/L	—	≥ 3 × ULN
ALT	U/L	—	≥ 3 × ULN
AST	U/L	—	≥ 3 × ULN
GGT	U/L	—	≥ 3 × ULN
LDH	U/L	—	≥ 3 × ULN
Blood urea nitrogen	mmol/L	—	> 1.2 × ULN
Calcium	mmol/L	< 0.9 × LLN	> 1.1 × ULN
Chloride	mmol/L	< 0.9 × LLN	> 1.1 × ULN
Cholesterol	mmol/L	—	> 1.3 × ULN
HDL	mmol/L	< 0.8 × LLN	—
LDL	mmol/L	—	> 1.2 × ULN
CPK	U/L	—	> 1.5 × ULN
Creatinine	μmol/L	—	> 1.3 × ULN
Glucose, fasting	mmol/L	< 0.8 × LLN	> 1.2 × ULN
Magnesium	mmol/L	< 0.9 × LLN	> 1.1 × ULN
Potassium	mmol/L	< 0.9 × LLN	> 1.1 × ULN
Sodium	mmol/L	< 0.9 × LLN	> 1.1 × ULN

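### Alternate-laboratory results stay out of the eCRF, so an abnormal on-treatment value can be absent from the PCS table or tabulated as a non-case

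*Protocol*

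**What the plan says.** **Rule for outside laboratories.** Protocol 12.2.4.2 allows a general practitioner's office or commercial laboratory to do the safety laboratory tests when the pandemic makes that necessary. It gives patient oversight as the purpose, and the result "will be filed in the source document only and not recorded in the eCRF".

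**Schedule and data route.** Protocol Table 3 (Section 6.6.3) schedules hematology, chemistry and urinalysis at visits "1 and Visit 6/ET". Section 6.7 names a central laboratory vendor and says that "ECG and laboratory data will be transferred to Allergan or its designee on a periodic basis throughout the study". Neither document describes a route for local values.

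**Tables (SAP 10.2).**
- PCS values: "The percentages will be calculated relative to the number of participants with available non-PCS baseline values and at least 1 postbaseline assessment".
- Descriptive statistics: "Only participants with clinical laboratory data at baseline and at least one postbaseline visit during the double-blind period will be included in the summary".
- Lipid and glucose changes: these "will be tabulated by treatment group for the DB treatment period".
- Liver: counts meeting Hy's law and "Concurrent Elevations criteria in a 24-hour period will be tabulated by DB treatment group for the safety population".

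**Reporting.** Protocol 9.5 says of potential Hy's law cases that "Study site personnel must report every patient who meets these criteria", on an SAE/AESI form and a dedicated eCRF.

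**Retest.** Protocol 12.2.4.2 and Table 4 footnote a ask for an unscheduled laboratory test during safety follow-up. SAP 15.3 uses every postbaseline assessment to determine PCS values.

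**The concern.** A sample is taken on treatment, the site reads the result, and the analysis database never receives it. The usual reason for missing laboratory data, that nobody measured it, does not apply. With one scheduled postbaseline test, there is no second on-treatment value to fall back on.

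The laboratory safety tables could then leave out abnormalities the sites already know about. Nor would a reader of the study report see the gap. The COVID-19 summaries in SAP 16.2 count missed laboratory assessments but have no category for tests done locally, and SAP 15.3's promise to list all assessments cannot be kept for values that are not in the database.

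**Working it through.** The plan states no figure on this point, so there is none to reproduce. The check follows a local Visit 6/ET result to each table, then gives a scale under an assumed share.

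**1. Route.** Section 12.2.4.2 closes the eCRF to the result, and a local laboratory is not part of the central vendor's transfer (Section 6.7). The patient has no on-treatment laboratory value in the database.

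**2. Outcome by table.**

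| Table | No central retest | Central retest in follow-up |
|---|---|---|
| PCS values | Out of numerator and denominator | Back in, on the retest value; a non-case if the abnormality has resolved |
| Descriptive; lipid and glucose | Out | Still out, because both are limited to the double-blind period, which ends at Visit 6/ET (SAP 10.0) |
| Concurrent elevations | In the safety population; a local case is a non-case | Counted only if the retest still meets the criteria |
| Hy's law | In the safety population; case recorded on its own eCRF | Same; the table's data source is not stated |

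The concurrent-elevation row differs from the Hy's law row because the Section 9.5 form covers only the full set of three criteria. ALT or AST at 3 x ULN or more with bilirubin at 1.5 x ULN or more, without the rest, has no form of its own.

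**3. How firm the retest is.** It is a best-effort request. The wording does not settle whether it covers patients already tested locally or only those whose test was omitted. Section 12.2.5 asks for return when a remote Visit 6/ET lacked laboratory assessment, and a locally tested patient arguably had one. By schedule Visit 7 falls 71 - 43 = 28 days after Visit 6, 74 - 43 = 31 days at the +3-day limit, and 78 - 43 = 35 days at the COVID-19 +7-day limit. If the last dose is taken at about Visit 6, a retest at Visit 7 can fall outside the 30-day Hy's law window of Protocol 7.3.3.2.

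**4. Scale (illustration).** Let f be the share of an arm of 250 with only a local postbaseline result and no central retest. The documents do not give f; the values below are assumptions. The PCS denominator is at most n = 250(1 - f). The chance of at least one event at a true rate of 1% is 1 - 0.99^n, and the one-sided 95% upper bound with zero events is 1 - 0.05^(1/n).

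| f | n | Chance of at least 1 event | Zero-event upper bound |
|---|---|---|---|
| 0 | 250 | 91.9% | 1.19% |
| 5% | 238 | 90.9% | 1.25% |
| 10% | 225 | 89.6% | 1.32% |
| 20% | 200 | 86.6% | 1.49% |
| 30% | 175 | 82.8% | 1.70% |

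If local-only patients have the same risk as the others, the PCS percentage is not biased, only less precise. If their risk differs, it is biased. With f = 10% and assumed PCS rates of 20% in local-only patients and 6% in the rest, the true rate is 0.9 x 6% + 0.1 x 20% = 7.4%. The table shows 6.0%, and 250 x 0.1 x 20% = 5 cases are lost.

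In the concurrent-elevation table the denominator stays at the safety population. At equal risk the apparent rate is (1 - f) times the true rate, so 10% too low in relative terms at f = 10%.

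**The case against.** The strongest case against is that this is a stated choice. One central laboratory gives one set of methods and ranges, the outside laboratory is a pandemic fallback meant for patient oversight, and mixing results from many small laboratories has a cost. That argument stands for mean changes. It is weak for criteria expressed as multiples of the laboratory's own limits, which is how Table 10-1 defines every chemistry criterion, hemoglobin and hematocrit.

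Abnormal results also have other ways in. An abnormal laboratory finding can be an adverse event (Protocol 9.1.1) and then goes in the eCRF. This is true, but an adverse event term does not enter a PCS or concurrent-elevation count.

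Three stronger readings are tempting, and the documents do not support them:
- *Hy's law patients disappear.* They do not. The denominator is the safety population, and Section 9.5 requires a dedicated eCRF and an SAE/AESI form without limiting the duty to central results. What remains is that the SAP does not name the data source for the table.
- *Every locally tested patient is lost from the PCS table.* A central retest in follow-up brings the patient back under SAP 15.3. The loss is confined to patients with no central postbaseline value.
- *A very high local ALT alone would be missed by the Hy's law and concurrent-elevation tables.* Both also need raised bilirubin, so an isolated ALT elevation belongs in neither. It bears on the PCS table, where the ALT criterion is 3 x ULN or more.

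**Conclusion.** The point holds in a limited form. The rule in Section 12.2.4.2 removes known on-treatment results from the analysis database. Without a central retest the patient is missing from the PCS table; with a normal later retest the patient is a PCS non-case despite an abnormal result in source. A local concurrent elevation short of Hy's law is tabulated as a non-case unless a central sample also shows it. For Hy's law itself the gap is one of specification: the case is on an eCRF that the SAP does not say it will use.

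The size is unknown, because the share tested only locally and the share retested are not given. On the assumed shares the loss of detection is small at 10% and more noticeable at 30%. The differential-risk example rests on assumed rates and shows a possible direction, not an estimate. The primary efficacy conclusion is not affected. This is a cheap improvement to the safety reporting.

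**What to change.** **Protocol 12.2.4.2.** Have alternate-laboratory results entered as local-laboratory data: value, unit, date and that laboratory's reference range.

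**SAP 10.2.**
- Count local values in the Hy's law and concurrent-elevation tables, and in the Table 10-1 criteria expressed as multiples of ULN or LLN.
- State that cases recorded on the Hy's law eCRF are included in the Hy's law table.
- List all local results with a flag.
- Keep local values out of the mean-change tables. Patients tested only locally stay missing there, which is the accepted price of a single central method, and the flagged listing makes that visible.

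**Cost.** One eCRF form, data entry for affected patients only, unit and range cleaning, and a few sentences in each document. No additional test is needed, because the result already exists in source.

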12.2.4.3 Electrocardiogram (ECG)

If visit is being performed remotely, this assessment may be omitted at the protocol-specified timepoint. Every attempt should be made to have patient complete as an Unscheduled assessment during the Safety Follow-up (SFU) period. Clinical findings upon termination must be followed until the condition returns to prestudy status or can be explained as unrelated to investigational product. If necessary, an additional follow-up visit should be scheduled.

12.2.4.4 Physical Examination

If visit is being performed remotely, this assessment may be omitted at the protocol-specified timepoint. Every attempt should be made to have patient complete as an Unscheduled assessment during the SFU period. Clinical findings upon termination must be followed until the condition returns to prestudy status or can be explained as unrelated to investigational product. If necessary, an additional follow-up visit should be scheduled.

12.2.4.5 Vital Signs

If visit is being performed remotely, this assessment may be omitted at the protocol-specified timepoint. Vital signs should be obtained at the next scheduled in-home or in-person visit.

12.2.5 Visit 6/ET- End of Double-Blind and Early Termination Visit

Every attempt should be made to complete the Visit 6/ET efficacy, safety and health outcome assessments on the same date. In the event that a remote visit for Visit 6/ET is not possible at the scheduled timepoint, all Visit 6/ET efficacy assessments should be completed within 2 weeks of the last dose of IP. If Visit 6/ET is completed as a remote visit without the assessment of clinical laboratory parameters (including pregnancy testing, if applicable), physical examination and/or ECG, the patient should be brought back for safety assessments during the SFU period. Patients who have missed the safety assessments scheduled for Visit 6/ET and are unable to return for these assessments during the SFU period should be encouraged to return to the site for a final assessment of safety when possible. All attempts should be made to make a final assessment of safety even if it falls beyond the end of the Safety Follow-up period. If Visit 6/ET procedures are being completed more than 2 weeks after the last dose of IP, efficacy assessments should be omitted.

12.2.6 Treatment compliance

Investigational Product compliance is to be assessed at every visit during the Double-Blind Treatment period. Wherever possible, IP compliance will be closely monitored by counting the number of capsules dispensed and returned, and through patient interview. For remote visits where a pill count by site staff may not be possible, patient reported compliance is to be documented. If a remote visit is occurring through a video/telemedicine virtual call, study staff should make every effort to visually verify number of capsules remaining in the blister card. Otherwise, patient reported verification of IP capsules remaining should be documented in the source.

To minimize undue burden on the patient, IP return may be less frequent during the time that visits are being conducted remotely but should occur no less frequently than monthly.

Background ADT medication compliance is also to be assessed at every visit. Patients should be questioned to determine if there were any missed doses or changes in dose between visits. Every effort should be made to have patients bring their background ADT to in-person study visits for verification of patient-reported compliance by pill/capsule count (to the extent possible) and patient interviews. For remote visits where a pill count by site staff may not be possible, patient reported compliance is to be documented.

Patients who take less IP or ADT or more IP or ADT than the prescribed regimen must be counseled on the importance of taking study medications as instructed. If a patient demonstrates poor compliance during the study (< 80% or > 120% overall), the investigator should evaluate whether the patient should be discontinued from the study. It is recognized that patients may miss doses of investigational product or his/her ADT due to circumstances related to COVID-19 (eg, unanticipated study window extension, delay in receipt of IP shipment from site to patient). There will be an allowance of up to 7 consecutive missed doses before requiring that a patient be discontinued from the study. The PI must ensure that the reason for missed doses is adequately assessed and determined to be related to logistical challenges related to COVID-19 and not that the reason is related to a causally-related adverse event, general non-adherence with the protocol, etc. Given the aforementioned concession, patients missing 4 or more doses should not be automatically withdrawn from the study treatment and the study as a result of the pandemic.

The study centers will continue to keep an accurate drug disposition record that specifies the amount of IP dispensed to each patient and the date of dispensing.

Table 4 COVID-19 Modified Schedule of Visits and Procedures (Applicable to Randomized Patients who have completed Visit 2)

Study Period	Screening	Baseline	Double-blind Treatment				Safety Follow-up
Visit	1	2	3	4	5	6/ET	7
Study Week	Up to -2	0	1	2	4	6	10
Study Day*	Up to -14	1	8	15	29	43	71
COVID-19 Informed Consent/Reconsent (where applicable)			(X)	(X)	(X)	(X)	(X)
Clinical Laboratory Tests ^a						X	
Serum Pregnancy Test ^a						X	X
Vital Signs ^b			X	X	X	X	X
Electrocardiogram ^c						X	
Physical Examination ^c						X	
HAMD-17						X	
YMRS						X	
MADRS			X	X	X	X	
CGI-S			X	X	X	X	
CGI-I			X	X	X	X	
HAM-A				X		X	
SF-12 ^d						X	
BARS/AIMS/SAS ^e			X	X	X	X	
C-SSRS ^f			X	X	X	X	X
Adverse Events			X	X	X	X	X
Concomitant Medications			X	X	X	X	X
Access IWRS for IP assignment			X	X	X		
Dispense IP ^g			X	X	X		
IP Compliance and Accountability ^h			X	X	X	X	
ADT Compliance ^h			X	X	X	X	
IP Return ⁱ			X	X	X	X	
Pharmacokinetic Sample (at any time during visit) ^j				X	X	X	
Pharmacogenetic Consent					X		
Pharmacogenetic Sample ^l					X		

Refer to Global Protocol or Country-Specific Amendment for Visit 1 Procedures

Refer to Global Protocol or Country-Specific Amendment for Visit 2 Procedures

*Note: If necessary, Visits 3 to 7 may be conducted up to 3 days before or after the scheduled visits. The visit windows for each scheduled visit are relative to Visit 2 for Visits 3 through 7. **In extenuating circumstances, the visit window for Visits 3 to 7 (inclusive) may be extended an additional 4 days (ie, +7 days) from the scheduled visit. All attempts should be made to conduct the visit within the pre-defined ± 3 day window as well as to avoid a potential lapse in IP during the extension of a visit window.**

ADT = antidepressant therapy; AIMS = Abnormal Involuntary Movement Scale; BARS = Barnes Akathisia Rating Scale; CGI-I = Clinical Global Impression–Improvement; CGI-S = Clinical Global Impression–Severity; C-SSRS = Columbia–Suicide Severity Rating Scale; ET = early termination; HAM-A = Hamilton Anxiety Rating Scale; HAMD-17 = Hamilton Depression Rating Scale–17 items;

IP = investigational product; IWRS = interactive web-response system; MADRS = Montgomery–Åsberg Depression Rating Scale; PI = Principal Investigator; SAS = Simpson–Angus Scale; SF-12 = Short Form-12 v2 Health Survey; WOCBP = women of child-bearing potential; YMRS = Young Mania Rating Scale. .

- ^a Clinical laboratory assessments, including serum pregnancy testing (WOCBP only) may be performed at an off-site laboratory facility if needed. If patient is unable or unwilling to travel to an alternate laboratory facility, the laboratory assessment at the scheduled timepoint may be omitted. For WOCBP, study sites may provide urine pregnancy test kits for at-home testing. Study personnel should document the patient's verbal confirmation of pregnancy test results in the source document. Patient should have clinical laboratory testing performed as an Unscheduled assessment during the Safety Follow-up period. Clinical findings upon termination must be followed until the condition returns to prestudy status or can be explained as unrelated to investigational product. If necessary, an additional follow-up visit should be scheduled.
- ^b If visit is being performed remotely, this assessment may be omitted. Vital signs should be obtained at the next scheduled in-home or in-person visit.
- ^c If visit is being performed remotely, this assessment may be omitted at this timepoint. Patient should have this assessment performed as an Unscheduled assessment during the Safety Follow-up period. Clinical findings upon termination must be followed until the condition returns to prestudy status or can be explained as unrelated to investigational product. If necessary, an additional follow-up visit should be scheduled.
- ^d If visit is being performed remotely, study staff should verbally administer the Short-Form 12 (SF-12) to the patient and record the patient's responses in the source.
- ^e Movement scales may be conducted remotely if needed. Where possible, telemedicine virtual visits or video calls (without recording) should be used to conduct this assessment remotely. If a scale item cannot be assessed, the item may be skipped and the source should indicate the item could not be assessed. Movement scales may only be conducted by raters certified on the scale.
- ^f C-SSRS may be assessed remotely if needed by a certified rater. Clinicians with a valid C-SSRS certification for another Allergan study may rate C-SSRS in the event the study-certified rater is unavailable to complete the assessment.
- ^g As an alternative to in-person drug dispensing, IP may be dispensed via a secure delivery method (where permissible by local, statutory, federal/country law) and after approval by Sponsor.
- ^h Assessment of compliance should be performed at each visit. For remote visits where a pill count by site staff may not be possible, patient reported compliance is to be documented. Patient reported verification of IP capsules remaining should be documented.
- ⁱ To minimize undue burden on the patient, IP return may be less frequent during the time that visits are being conducted remotely but should occur no less frequently than monthly.
- ^j If visit is being performed remotely or at an alternate laboratory facility, this assessment may be omitted. In consideration of the processing time required, pharmacokinetic samples should not be collected during in-home visits.
- ^k Pharmacogenetic consent may be obtained at any time between Visit 1(Screening) and Visit 6 (Week 6). Pharmacogenetic consent may not be obtained remotely.

¹ Pharmacogenetic sample (1 per patient for the entire study) may be obtained from randomized patients at any time between Visit 2 (Baseline) and Visit 6 (Week 6). To be omitted if sampling is not possible due to remote visits being completed.

